3. STUDY DESIGN

3.1 DESCRIPTION OF THE STUDY

Study BN40031 is a Phase III, OLE, multicenter study to evaluate the long-term safety and tolerability of crenezumab at a dose of 60 mg/kg IV Q4W in patients with AD who have participated in one of the Phase III *parent studies* (BN29552 or BN29553). Efficacy will also be assessed. Patients who discontinued early from study treatment during Study BN29552 or BN29553 but remained in the study for safety and additional efficacy evaluations and completed the Week 105 study visit can enter the OLE study and begin open-label treatment. Patients from Study BN29552 or BN29553 who discontinued the study prior to completion of the Week 105 study visit are not eligible for this OLE study.

Studies BN29552 and BN29553 are ongoing Phase III, multicenter, randomized, double-blind, placebo-controlled, parallel-group, efficacy and safety studies of crenezumab in patients with pAD to mAD. The planned number of patients for this OLE study is not expected to exceed 1500 (approximately 750 randomized to crenezumab 60 mg/kg IV and 750 randomized to placebo, i.e., the total planned number of patients in the *parent studies* BN29552 and BN29553, not including patients from the China extension study). An estimate for the actual number of patients in this OLE study is approximately 925 patients (*not including patients from the China extension study*) based on 1500 patients enrolled in both Phase III studies and an estimated reduction by 35% (i.e., withdrawals from double-blind treatment) and by a further 5% of completers who may not opt to enroll in this OLE study. Approximately 350 centers in approximately 40 countries worldwide will participate in this study.

Patients and all clinical site staff will remain blinded to the original treatment assignment in Studies BN29552 and BN29553 on entry into the OLE study and until a later time which will be determined by the Sponsor.

Following completion of the global enrollment phase of Study BN29553, additional patients will continue to be enrolled in a China extension phase (i.e., China extension to the main Phase III study BN29553) to ensure a total enrollment sufficient to support registration in the People's Republic of China. This China subpopulation may include patients enrolled at sites in China during both the global enrollment phase and the China extension phase and could be included in this OLE, if applicable.

3.2 STUDY DESIGN

All patients who are enrolled in the OLE study will receive crenezumab 60 mg/kg administered by IV infusion Q4W.

Data collected at Week 105 of the DBTP of Studies BN29552 and BN29553 and results from a coagulation blood test taken before the first OLE infusion will be used to assess patient eligibility for the OLE study. This Week 105 data will also be used as OLE baseline data.

Prior to administering the first infusion in the OLE, eligibility will be ensured by reviewing Week 105 assessment results (*including MRI results*), *OLE screening* coagulation blood test results, and any other significant patient changes.

Once a patient is identified as eligible for the OLE study, the following will occur:

- Patients can receive the first infusion of crenezumab at any time on or up to 8 weeks after the Week 105 visit of the double-blind studies. Any extensions to this period must be approved by the Sponsor. Sites can arrange an infusion visit as soon as *eligibility assessment results* are available (including MRI results and results from the coagulation test) to assess OLE eligibility. Details of the visit schedule and associated assessments are given in [Appendix 1](#).
- The day that the first dose of crenezumab is administered will be Visit 1, Week 1 of the OLE.
- On Visit 1, Week 1 of OLE (i.e., the first open-label infusion of crenezumab), safety assessments must be done as indicated in the schedule of activities (see [Appendix 1](#)).

For details on the schedule of activities, see [Appendix 1](#). For details on the length of the study, see Section [3.3](#).

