1.2.5 Pharmacokinetics

The pharmacokinetics of crenezumab have been evaluated in five Phase I studies (ABE4427g, ABE4662g, GP29172, [REDACTED] and GN29632) and in two Phase II studies (ABE4869g and ABE4955g). Overall, the observed serum pharmacokinetics in the Phase I and II studies have appeared to be dose proportional (IV: 0.3–10 mg/kg single dose and 15–120 mg/kg Q4W; SC: 1.8 mg/kg single dose and 600–7200 mg single dose) and the PK parameters (e.g., clearance [CL], half-life [$t_{1/2}$]) in the Phase I studies have been consistent with those for other humanized IgG MABs that exhibit kinetics in the linear concentration range (Mould and Sweeney 2007; Dirks and Meibohm 2010; Deng et al. 2011).

In the Phase I study ABE4427g, the serum pharmacokinetics of crenezumab in patients with mild to moderate AD were dose proportional across the dose range tested in both the single-dose (0.3–10 mg/kg) and multi-dose (0.5–5 mg/kg weekly for four doses) phases of the study. Crenezumab CL was slow (2.5–3.3 mL/day/kg) with a long terminal $t_{1/2}$ (17–26 days) following a single IV dose. With weekly administration, there did not appear to be any time-dependent change in crenezumab pharmacokinetics relative to single-dose administration, as evidenced by similar terminal elimination $t_{1/2}$ estimates (18–23 days) relative to the single-dose arm. [REDACTED]

The Phase I study GP29172 demonstrated that crenezumab serum PK parameters following administration of the Phase III drug product (180 mg/mL) were bioequivalent to the Phase II drug product (150 mg/mL) following a single 720-mg SC injection in healthy volunteers. These results were supportive of a change of drug product in ongoing clinical studies.

[REDACTED]

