6.5 EFFICACY ANALYSES

All efficacy data during the open-label study will be summarized using descriptive statistics for the ITT population. Observed values and change from the OLE baseline values at each scheduled visit will be summarized.

For all continuous safety parameters, efficacy parameters, and biomarkers, *descriptive statistics for the change from baseline will be generated using the baseline value for the*

OLE study (defined as the last value recorded during the DBTP). *Descriptive statistics may also be generated for the change from the DBTP baseline.*

All efforts will be made to minimize missing data. Descriptive summaries of the number of patients with missing data and the timing and reasons for discontinuation from study will also be provided. Additional details will be documented in the SAP.

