6.5.2 Exploratory Efficacy Analyses

An analysis of the change from baseline in CDR-SB values recorded during the DBTP in Studies BN29552 and BN29553 and at specified timepoints of the OLE study will be performed. In this case, a mixed-effect model for repeated measures (MMRM) will be used to compare the change from the double-blind baseline at OLE timepoints, relative to the change from the double-blind baseline to the end of double-blind treatment. This analysis will compare the patients randomized to placebo during the DBTP (delayed start patients) with those randomized to crenezumab during the DBTP (early start patients). This analysis will be performed using all data from the ITT populations of Studies BN29552 and BN29553 as well as the ITT population from the OLE study. Details of this analysis will be specified in the SAP.

The effect of randomization stratification factors (dementia status [pAD vs. mAD], patient APOE4 status [presence or absence of ϵ 4 allele], background medication at baseline [present, absent], and geographic region) may be explored by adding each of these covariates to *this* MMRM model.

Subgroup analysis of efficacy results will also be performed for subgroups defined by age, sex, race, dementia status (pAD vs. mAD), APOE4 status, geographic region, use and non-use of background therapies for AD, and other clinically relevant factors at baseline.

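### Change from OLE baseline is measured from parent Week 105 but labelled by weeks since first infusion, so nominal-visit changes include up to 8 weeks (or more) of decline before any open-label dose

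*Combined protocol and SAP*

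**What the plan says.** Protocol Section 3.2 sets two different origins.

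- **Baseline.** Of the parent Week 105 visit it says: "This Week 105 data will also be used as OLE baseline data". Section 6.5 defines the OLE baseline value as "defined as the last value recorded during the DBTP", which is normally the same assessment.
- **Clock.** "The day that the first dose of crenezumab is administered will be Visit 1, Week 1 of the OLE".
- **Distance between them.** "Patients can receive the first infusion of crenezumab at any time on or up to 8 weeks after the Week 105 visit". The Sponsor may approve a longer period, and no maximum is given. Section 4.5.11 repeats the 8-week window.
- **No new baseline at first dose.** Section 3.2 asks for safety assessments at Visit 1. In Appendix 1 the CDR, ADAS-Cog-13, ADCS-ADL/FAQ and MMSE are first scheduled at OLE Week 25.
- **Descriptive analysis.** The exploratory efficacy endpoints in Section 2 are changes from baseline during the OLE. Section 6.5 states: "Observed values and change from the OLE baseline values at each scheduled visit will be summarized".
- **Delayed-start analysis.** The MMRM in Section 6.5.2 has a different reference. It will "compare the change from the double-blind baseline at OLE timepoints", setting that against the change to the end of double-blind treatment.

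Neither analysis section mentions the gap or actual elapsed time. Both leave further detail to a SAP.

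**The concern.** Alzheimer's disease progresses steadily, and Section 3.4.2 expects continued cognitive decline in this population. A change measured from Week 105 but labelled by weeks since first infusion therefore includes whatever decline took place in between. The gap cannot be negative, so the error runs one way: the summary shows more decline than occurred during open-label treatment. The same nominal visit also stands for different lengths of follow-up in different patients.

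Some gap is likely for many patients. Dosing has to wait for review of the Week 105 MRI and a coagulation result. The amendment summary says the window was widened from 4 to 8 weeks to give sites time to confirm eligibility and flexibility in scheduling. A reader who sets the Week 53 OLE change against a 52-week change from another source would be comparing unequal periods.

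**Working it through.** **Week convention.** The plan gives no elapsed time from OLE baseline, so the convention is checked first. Section 1.3.2 places an MRI about 12 weeks after the first dose, and the schedule calls that visit Week 13. Section 1.3.3 gives 26 doses over 104 weeks: 26 × 4 = 104, which leads to a Week 105 visit. Both agree with nominal Week n = n − 1 elapsed weeks.

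**Inputs.** Gap g from Week 105 to first infusion: 0 to 8 weeks (Section 3.2). Visit window on dosing days: ±7 days (Appendix 1). Rate of CDR-SB worsening: 1 to 2 points a year, which is an assumption and not a figure in the documents.

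**Elapsed time.** Weeks from OLE baseline = (n − 1) + g. Excess over nominal = g / (n − 1).

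| OLE visit | g = 0 | g = 4 | g = 8 |
|---|---|---|---|
| Week 25 | 24 | 28 (+17%) | 32 (+33%) |
| Week 53 | 52 | 56 (+8%) | 60 (+15%) |
| Week 105 | 104 | 108 (+4%) | 112 (+8%) |

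The right-hand column is the maximum for the standard window at the nominal visit day. The ±7-day window raises Week 25 and Week 53 to 33 and 61 weeks. A Sponsor-approved gap of 12 weeks (assumed for illustration) would give 36 and 64.

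**CDR-SB points added before the first open-label dose.** Excess = rate × g / 52.

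- g = 4: 1 × 4/52 = 0.08; 2 × 4/52 = 0.15.
- g = 8: 1 × 8/52 = 0.15; 2 × 8/52 = 0.31.

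**Delayed-start MMRM.** Weeks from the double-blind baseline to OLE Week 53 = 104 + g + 52, that is 156 (g = 0) to 164 (g = 8). To see whether this spread matters for precision, assume gaps uniform over 0–8 weeks. Their SD is 8/√12 = 2.3 weeks, or 2.3/52 × (1 to 2) = 0.04 to 0.09 points. Against an assumed SD of change of 1.5 to 3 points, the variance rises by between (0.044/3)² = 0.02% and (0.089/1.5)² = 0.35%. That is negligible.

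**The case against.** The strongest reply has four parts.

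1. *These are exploratory, descriptive summaries without a hypothesis test, and the primary objective is safety.* This stands, and it limits the importance of the point.
2. *The 8-week figures are extremes.* This also stands. Sites may infuse as soon as eligibility results are in, a patient dosed on the Week 105 visit day has no gap, and Section 4.5.11 allows Week 105 assessments to be completed at an unscheduled visit before OLE Week 1, which shortens the interval. Hence the 4-week figures.
3. *Details are left to the SAP.* This does not answer the point. Section 6.5 already fixes summaries by scheduled visit, and a SAP is where the correction belongs.
4. *Counting from first infusion is deliberate.* For the delayed-start comparison this is right. Section 1.3.3 defines Period 2 by years of OLE treatment and wants enough time for crenezumab to act in former placebo patients. OLE visits align that exposure; weeks since randomisation would mix it.

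A reader might go further and infer that the gap undermines the delayed-start comparison: former crenezumab patients lose exposure, so a shrinking early-start advantage might reflect the pause. With the 17–26 day half-life in Section 1.2.5, 56 days without dosing would leave 2^(−56/17) = 10% to 2^(−56/26) = 22% of the Week 105 level. The documents do not carry the inference. The MMRM starts from the double-blind baseline, both former arms follow the same gap rule, and Section 3.1 keeps patients and sites blinded to parent assignment at entry. Neither arm is dosed during the gap. An accrued disease-modifying difference should survive a short pause, and one that vanished in it would itself suggest a reversible effect. Section 1.2.5 puts Phase II steady-state troughs at Weeks 13–25, and the comparison falls after 1 or 2 years of OLE treatment. Nor can a single time since last dose be assigned at OLE entry: Section 3.1 admits patients who stopped parent treatment early, and the parent dosing schedules are not in these documents.

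**Conclusion.** The point holds for the change-from-OLE-baseline summaries in Section 6.5. Within the standard window they cover up to 8 weeks more than their label, all of it before the first open-label dose, so they overstate decline during open-label treatment. The relative excess is largest at Week 25 and fades by Week 105. The direction follows from the protocol's own rules plus continued decline. The size in points depends on the assumed rate, roughly linear worsening, and a gap distribution that the documents do not give.

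For the delayed-start MMRM no between-arm bias is shown. The gap only spreads the true time of each OLE visit, and a difference in gap between the former arms is not expected but is not checked either. This is an inexpensive improvement to exploratory results and does not touch the primary safety objective.

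**What to change.** **Section 6.5.** Beside the nominal-visit summary, report change from OLE baseline using actual elapsed time since the Week 105 assessment: either a rate per actual time, or a model with actual time or the gap as a covariate. Use the date on which each scale was done, since Week 105 assessments may be completed at a later visit. Tabulate the Week 105-to-first-infusion gap by original arm.

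**Section 6.5.2.** Keep the planned MMRM at OLE visits. Add one sensitivity analysis that uses actual time since the double-blind baseline, or the gap as a covariate.

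Two alternatives are not recommended. Re-windowing every visit to weeks since randomisation as the main analysis would give up aligned open-label exposure. Restricting the delayed-start comparison to patients with short gaps would select on a post-randomisation variable.

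**Cost.** SAP wording, slightly more programming and one extra sensitivity table. No new visits or assessments are needed; the work uses visit and dosing dates.

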3.2.1 Independent Data Monitoring Committee

The incidence and nature of adverse events, serious adverse events, adverse events of special interest, ARIA-E and ARIA-H abnormalities, ECG findings, vital signs, and laboratory abnormalities will be assessed on a regular basis by an iDMC. It is anticipated that these assessments will occur approximately every 3 months until Studies BN29552 and BN29553 are unblinded.

The details of iDMC will be provided in the iDMC Charter.

3.3 END OF STUDY AND LENGTH OF STUDY

The OLE study will continue until crenezumab is commercially available in the patient's country, as per local regulation, or should the Sponsor decide to terminate the program for *pAD* to *mAD*. *However, all patients will have the opportunity to complete approximately 2 years of treatment even if crenezumab is commercially available in the patient's country.* The study will not exceed approximately 2 years after the last patient enrolled during the global enrollment phase (in Study BN29552 or BN29553) enters the OLE study.

For United Kingdom only: The OLE study will not exceed approximately 2 years after the last patient *enrolled during the global enrollment phase in Study BN29552 or BN29553* enters the OLE study or until a decision to terminate the program for pAD to mAD is made by the Sponsor.

For the first patient entering the OLE study, the maximum duration would be approximately 4 years, depending on the date of commercialization or the date of the last patient enrolled in Study BN29553 (12 July 2018).

The 2-year duration of the OLE study serves to evaluate long-term safety, tolerability, and efficacy of crenezumab treatment in patients with AD and allows for all patients to reach the 2-year treatment duration in the OLE study for the efficacy analysis.

Patients who discontinue crenezumab treatment during Year 1 of the OLE study will be followed for 16 weeks after their last dose of crenezumab and will also be asked to complete the remaining scheduled efficacy assessments at Week 53 of the OLE as per the schedule of activities (see [Appendix 1](#)).

Patients who discontinue crenezumab treatment during Year 2 of the OLE study will be followed for 16 weeks after their last dose of crenezumab and will also be asked to complete the remaining scheduled efficacy assessments at Week 105 of the OLE as per the schedule of activities (see [Appendix 1](#)).

Patients who discontinue treatment after Year 2 (Week 105) of the OLE study will be followed up for safety for 16 weeks. Patients who complete the OLE study and continue treatment with crenezumab thereafter will not be followed up.

Patients and sites will remain blinded to their assignment in Study BN29552 or BN29553 until permitted by the Sponsor.

Every effort should be made to have the same caregiver participate throughout the duration of the OLE study who also participated in Study BN29552 or BN29553. If the caregiver cannot continue to participate in the OLE study and cannot be replaced, the patient can continue in the OLE as long as patient safety can be assured.

The end of this study is defined as the date when the last patient, last visit occurs or the date at which the last data point required for statistical analysis or safety follow-up is received from the last patient, whichever occurs later. The end of the study is expected to occur approximately 28 months after the last patient is enrolled.

The total length of the study, from screening of the first patient to the end of the study, is expected to be approximately 4 years.

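### Does Section 3.3 contradict itself on who can reach 2 years of OLE treatment if China-extension patients enter the OLE?

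*Combined protocol and SAP*

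**What the plan says.** Section 3.3 contains three statements that bear on this point.

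- The cap: "The study will not exceed approximately 2 years after the last patient enrolled during the global enrollment phase" enters the OLE.
- A rationale sentence: the 2-year duration "allows for all patients to reach the 2-year treatment duration in the OLE study for the efficacy analysis".
- A sentence on market launch: "all patients will have the opportunity to complete approximately 2 years of treatment even if crenezumab is commercially available" in the patient's country.

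Section 3.1 says that, once global enrolment in Study BN29553 is complete, "additional patients will continue to be enrolled in a China extension phase", and that the China subpopulation "could be included in this OLE, if applicable". The headcount in the same section is given as "not including patients from the China extension study". Section 3.2 allows the first OLE infusion "at any time on or up to 8 weeks after the Week 105 visit" of the parent study, with longer gaps subject to Sponsor approval.

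Section 3.3 also expects the study to end about 28 months after the last patient is enrolled, without saying which last patient. It gives 12 July 2018 as the date the last patient was enrolled in Study BN29553. Section 6.6 plans to look at long-term effects in the China subpopulation and their consistency with the global population. It leaves the methods to the SAP and puts the results in a separate report.

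**The concern.** The cap is anchored to a global-phase patient, and the two sentences about all patients have no such anchor. Extension patients enrol later, serve the same 104-week double-blind period, and would share the stop date of patients who started before them. Beyond a short lag, the cap and an unrestricted promise of 2 years cannot both hold for them. The protocol excludes the extension in words when it gives the headcount, and Section 3.3 has a paragraph for the United Kingdom but none for China. The silence could therefore be read as inclusion.

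If so, a reader could miscount who can supply 2-year OLE data. A China-versus-global comparison at OLE Week 105 could also mix patients who had access to that visit with patients who did not.

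**Working it through.** **The plan's own figure.** Two years of treatment plus the 16-week follow-up is 104 + 16 = 120 weeks, or 120 × 7 / 30.44 = 27.6 months. This reproduces the 28 months in Section 3.3 when counted from the last global-phase patient's OLE entry. It also shows that the cap can be read as ending dosing, with follow-up visits after it.

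**Set-up.** Let L be the number of weeks by which an extension patient's parent-study enrolment trails that of the last global-phase patient. Let dG and dE be the delays from parent Week 105 to first OLE dose for the global-phase and the extension patient, each 0 to 8 weeks (Section 3.2). Both patients spend 104 weeks in double-blind treatment (Section 1.3.3).

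- Cap: 104 + dG + 104 weeks after the last global-phase enrolment.
- Extension patient's first OLE dose: L + 104 + dE weeks on the same clock.
- OLE time before the cap: 104 − L + (dG − dE) weeks.

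Assume that 12 July 2018 is the last global-phase enrolment and parent Day 1. The last global-phase patient then enters the OLE between 9 July and 3 September 2020, and the cap falls at about July to September 2022.

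**Largest lag that still allows 2 years.** There are two readings of the cap.

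- *Week 105 visit before the cap:* L ≤ dG − dE.
- *Last dose before the cap:* Section 1.3.3 counts 104 weeks as 26 doses. Dosing every 4 weeks from Week 1 puts dose 26 at Week 1 + 25 × 4 = 101, which is 100 weeks after the first dose. Appendix 1 schedules the main efficacy scales for completers 4 weeks after the last dose, which is about Week 105. Then L ≤ 4 + dG − dE.

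| Reading | Equal delays | Best case (dG = 8, dE = 0) | Worst case (dG = 0, dE = 8) |
|---|---|---|---|
| Week 105 visit before cap | 0 weeks | 8 weeks (1.8 months) | −8 weeks: no extension patient |
| Last dose before cap | 4 weeks (0.9 months) | 12 weeks (2.8 months) | −4 weeks: no extension patient |

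The 7-day visit window adds 1 week, so the best cases become 9 and 13 weeks (2.1 and 3.0 months). Each week of Sponsor-approved delay for the last global-phase patient, or of latitude in *approximately*, adds a further week.

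**One-year data.** OLE Week 53 is 52 weeks after the first dose, so L ≤ 52 + (dG − dE). That is 44 to 60 weeks, or 10.1 to 13.8 months.

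**Illustration with assumed lags.** A 6-month lag leaves 24 − 6 = 18 months of OLE time, and a 12-month lag leaves 24 − 12 = 12 months. Each moves by up to 1.8 months (8 weeks) with the first-dose delays, giving about 16 to 20 and 10 to 14 months.

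**What depends on it.**

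- *Primary objective.* Safety is summarised descriptively (Sections 6 and 6.4). No summary requires 2 years of treatment.
- *Headcount.* 1500 × 0.65 × 0.95 = 926, which matches the stated 925 or so and excludes the extension.
- *Delayed-start comparison.* Section 1.3.3 leaves Period 2 at 1 or 2 years. The repeated-measures model in Section 6.5.2 can use whatever visits a patient has. A stop fixed by calendar date depends on when a patient enrolled, not on randomised arm or outcome.
- *China analysis.* The methods, including the follow-up length to compare, belong to the SAP under Section 6.6.

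**The case for a change.** The strongest case for a change is that the tension lies within one section, and that Section 4.3.2.1 sends sites to that section to learn when dosing ends. An SAP can choose timepoints, but it cannot correct protocol text. The amendment summary says the China extension has been activated in the parent studies, so the condition is a live one. Appendix 1 separates patients who discontinue from patients who complete, and nothing names the patient stopped by the cap before Week 105.

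Some of this stands. The scope of the sentences about all patients is not stated, and the direction of the arithmetic does not depend on the assumed lags. The 28-month sentence leaves its last patient undefined; counted from the last extension patient, it would run past the cap plus follow-up by the length of the lag.

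The rest carries less weight. The operative limit is not in doubt, because the cap is the only rule that sets a maximum length. The sentence on the efficacy analysis explains a duration that the section has already tied to the global phase, so reading it as the global cohort is coherent. The sentence on market launch mainly addresses commercial availability. A patient dosed to study end most naturally counts as a completer, with the 4- and 16-week visits that Section 3.4.2 and Appendix 1 provide, and Section 4.3.4 covers conditional access afterwards.

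**Conclusion.** The scope of Section 3.3 is ambiguous, but this is not a fault in the design or analysis. If China-extension patients enter the OLE, those enrolled more than about 0 to 3 months after global enrolment closed could not complete 2 years before the cap. How many that would be is unknown, because the documents give neither enrolment dates nor numbers for the extension. The calendar dates rest on taking 12 July 2018 as the last global-phase enrolment and parent Day 1.

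The possible effect is confined to exploratory 2-year data in the China subpopulation. An analyst following the plan would treat cap-related endings as completion and compare populations over follow-up that both can reach, which the SAP is already charged with settling. Extra protocol text on these points would change no result. Patients enrolled in China during the global phase are unaffected, as are the primary safety results and the global cohort.

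The sponsor has to reconcile the cap with the sentences about all patients by saying whether each covers extension patients. That is a clarification of wording, and this review takes no position on how long anyone should be treated.
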